1.1 Objectives

- 1) To determine radiographic recurrence of hallux valgus and the timing of failure following hallux valgus correction with the Lapiplasty® Procedure.
- 2) To determine whether the Lapiplasty® Procedure effectively corrects anatomical alignment of the 1st metatarsal and sesamoids in all three planes.
- 3) To assess whether early weight-bearing (WB) after the Lapiplasty® Procedure affects the union rates or causes loss of 3-plane correction.
- 4) To evaluate the quality of life and pain scores following the Lapiplasty® Procedure.

1.2 Endpoints

1.2.1 Primary Endpoint

Proportion of subjects with radiographic recurrence of hallux valgus deformity (bunion recurrence) at 24 months, limited to subjects with successful correction at 6 weeks.

1.2.2 Secondary Endpoints

- 1) Change from baseline in radiographic angular/positional alignment at 6 weeks, 4 months, 6 months, 12 months, and 24 months post-Lapiplasty® Procedure.
- 2) Percentage of subjects with absence of clinical/radiographic healing, or non-union, at 12 months post-Lapiplasty® Procedure.
- 3) Clinical complications through 24-month follow-up visit due to the Lapiplasty® System Implants, the Lapiplasty® Procedure, the post-operative weight-bearing protocol or health conditions that could affect other outcome measures.
- 4) Time to start weight-bearing in boot, in days.
- 5) Time to start weight-bearing in shoes, in days.
- 6) Time to return to full unrestricted activity, in days.
- 7) Change from baseline in pain at the base of the big toe (bunion related) assessed via a Visual Analog Scale (VAS) at 0-14 days, 14-21 days, 6 weeks, 4 months, 6 months, 12 months, and 24 months.
- 8) Change from baseline in Quality of Life at 6 months, 12 months, and 24 months as measured by PROMIS-29 (for adult subjects), PROMIS-25 (for pediatric subjects), and MOxFAQ (for all subjects).
- 9) Change from baseline in range of motion (ROM) of 1st MTP dorsiflexion and plantarflexion at 12 months and 24 months.
- 10) Change, if any, in incision length during the Lapiplasty® Procedure.
- 11) Change from baseline in radiographic foot length and width at 12 months post-Lapiplasty® Procedure.
- 12) Change in swelling at 6 weeks and 4 months post-Lapiplasty® Procedure as compared to 0-14 day visit.
- 13) Change in scar quality at 4 months, 6 months, and 12 months post-Lapiplasty® Procedure.
- 14) Correlation between amount of time external positioner is actively used during Lapiplasty® Procedure with necrosis, blistering, bruising, and tissue ulceration events.

1.2.3 Health Economic and Safety Endpoints

All health economic endpoints are exploratory in nature.

- 1) Complications below that are related to the Lapiplasty® Procedure or the Lapiplasty® System Implants requiring subsequent secondary surgical interventions, defined as the following:
 - a) deviations/delay from normal operative plan
 - b) readmission to hospital
 - c) return to operating room
 - d) unscheduled visits due to complications
 - e) employment of home health services
 - f) revisions
 - g) hardware removals
 - h) reoperations
 - i) supplemental fixation
 - j) wound healing
 - k) infection at surgical site

- 2) Time to return to work (or normal household activities if non-working), in days, while noting work status and work classification (sedentary, light work, medium work, heavy work, very heavy work).
- 3) Time to return to full work (or normal household activities if non-working), in days, while noting work status and work classification (sedentary, light work, medium work, heavy work, very heavy work).
- 4) Percentage of subjects requiring post-operative physical therapy for recovery from the Lapiplasty® Procedure.

1.2.4 Exploratory Endpoints

Additional endpoints may be pursued at the time of analysis and will be exploratory in nature.

[figure not shown]
Study Methods

1.3 Overall Study and Design

This is a prospective, single-arm, multicenter, unblinded study. Subjects 14 years through 58 years with symptomatic hallux valgus are eligible to participate based on the inclusion and exclusion criteria defined below. The overall plan for all subjects consists of the following elements:

- Patients will be informed about the nature of the research, given the ICF to read, and if the patient understands and agrees to the procedure, they will be asked to provide written informed consent. Subjects are considered **enrolled** in the study when they have signed an informed consent;
 - Subjects will undergo screening procedures during the baseline visit to determine if inclusion and exclusion criteria are satisfied and the subject is eligible for the study procedure;
- Subjects must meet all inclusion/exclusion criteria before being **treated** in the study. If any eligibility criteria (including intra-operative criteria) are not satisfied, the subject will be considered a screen failure and will not be considered treated in the study;
- Subjects will undergo the Lapiplasty® Procedure, per protocol. Subjects are considered **treated** in the study when biplanar plating at the TMT joint is complete **and** the incision length is confirmed to meet criteria;
 - Subjects will be followed for up to 2 years post index procedure to evaluate outcomes and potential complications;
 - Subjects will be assessed for AEs and will be instructed to notify the PI of any AEs that occur during the entire course of the study. Data will be recorded into subject source medical records.

Subject Disposition Diagram

1.4 Inclusion-Exclusion Criteria

1.4.1 Inclusion Criteria

Subjects satisfying all the following inclusion criteria will be eligible for participation:

- 1) Male and females between the ages 14 and 58 years at the time of consent
- 2) Closed physeal plates at the time of consent
- 3) Intermetatarsal angle (IMA) between 10.0° - 22.0°
- 4) Hallux valgus angle (HVA) between 16.0° - 40.0°
- 5) Willing and able to adhere to early weight-bearing instructions post-operatively
- 6) Capable of completing self-administered questionnaires
- 7) Acceptable surgical candidate, including use of general anesthesia
- 8) Female subjects must be of non-childbearing potential or have a negative pregnancy test within 7 days prior to index procedure
- 9) Willing and able to schedule index procedure within 3 months of consent and able to return for scheduled follow-up visits
- 10) Willing and able to provide written informed consent

1.4.2 Exclusion Criteria

Subjects satisfying any one of the following exclusion criteria will not be eligible for participation:

- 1) Previous surgery for hallux valgus on operative side
- 2) Previous surgeries on operative foot involving fusion of foot or ankle joints (other than hammertoe or lesser toes/digits)
- 3) Additional concomitant procedures outside of the 1st ray
- 4) Moderate or Severe osteoarthritis of the MTP joint based on radiographic imaging (including lack of evident crista) or positive grind test
- 5) Symptomatic flatfoot or asymptomatic flatfoot (defined as calcaneal inclination <5° and talonavicular subluxation/uncovering >50%)
- 6) BMI >40 kg/m²
- 7) Current nicotine user, including current use of nicotine patch

- 8) Current clinical diagnosis of diabetes with fasting plasma glucose >126 mg/dL and/or HbA1c ≥ 7.0
- 9) Current clinical diagnosis of peripheral neuropathy or by assessment on 4-point monofilament test
- 10) Current clinical diagnosis of fibromyalgia
- 11) Current clinical diagnosis of Complex Regional Pain Syndrome/Reflex Sympathetic Dystrophy (CRPS/RSD)
- 12) Current uncontrolled hypothyroidism
- 13) Previously sensitized to titanium
- 14) Currently taking oral steroids or rheumatoid biologics
- 15) Currently taking immunosuppressant drugs
- 16) Insufficient quantity or quality of bone to permit stabilization, conditions that retard healing (not including pathological fractures) and conditions causing poor blood supply such as peripheral vascular disease
- 17) Active, suspected or latent infection in the affected area
- 18) Use of synthetic or allogenic bone graft substitutes
- 19) Current diagnosis of metatarsus adductus (defined as MAA $\geq 23^\circ$)
- 20) Known keloid and hypertrophic scar forming
- 21) Scheduled to undergo a same-day bilateral procedure. Subject agrees to refrain from the Lapiplasty® Procedure (or other hallux valgus procedures) on contralateral foot for minimum of 6 months post index procedure
- 22) Subject has previously been enrolled into this study for a contralateral procedure;
- 23) Scheduled for any concomitant procedure that would alter subject's ability to early weight-bear post-procedure
- 24) Subject requires an incision >4.0 cm to complete the procedure (determined pre-operatively or intra-operatively)
- 25) Subject is actively involved with a workman's compensation case or is currently involved in litigation
- 26) Subject is currently or has participated in a clinical study in the last 30 days prior to signing informed consent or is considering participation in another research protocol during this study. Exceptions to this include survey clinical studies with no treatment or if subject is greater than 12 months post procedure in the Treace ALIGN3D™ study without ongoing protocol defined AE; these are not exclusionary
- 27) Subject has a condition or finding that, in the opinion of the Investigator, may jeopardize the subject's well-being, the soundness of this clinical study, or could interfere with provision of informed consent, completion of tests, therapy, or follow-up.

1.5 Schedule of Assessments

Study Activity	Visit 1	Visit 2	Visit 3	Visit 4	Visit 5	Visit 6	Visit 7	Visit 8	Visit 9	Study Exit
	Baseline ¹	Index Lapiplasty® Procedure	0-14 Day follow-up	14-21 Day follow-up	6 Week follow-up	4 Month follow-up	6 Month follow-up	12 Month follow-up	24 Month follow-up	
Informed Consent	X									
Demographics	X									
Medical and Surgical History	X	X								
Targeted Physical Exam	X									

Study Activity	Visit 1	Visit 2	Visit 3	Visit 4	Visit 5	Visit 6	Visit 7	Visit 8	Visit 9	Study Exit
	Baseline ¹	Index Lapiplasty® Procedure	0-14 Day follow-up	14-21 Day follow-up	6 Week follow-up	4 Month follow-up	6 Month follow-up	12 Month follow-up	24 Month follow-up	
Height / Weight ²	X									
Blood Collection, if required ³	X									
4-Point Monofilament Test, if required ⁴	X									
Radiographic Imaging ⁵	X				X	X	X	X	X	
VAS Pain Scale	X		X		X	X	X	X	X	
QOL Measurements ⁶	X						X	X	X	
Medications Review	X	X	X		X	X	X	X	X	
Digital Photos of Foot										
Clinical Exam of Foot	X		X		X	X	X	X	X	
Foot Measurements	X	X	X	X	X	X	X	X		
Pregnancy Test (if applicable) ⁷	X									
Inclusion/Exclusion Criteria	X ⁸	X ^{9, 10}								
Index Procedure		X								
Wound check/surgical site healing			X		X	X				
Return to Weight-Bearing Activities ¹¹			X		X	X	X			
Range of Motion ¹²	X					X	X	X	X	
Secondary Surgical Interventions ¹³			X		X	X	X	X	X	
Adverse Events Assessment ¹⁴		X	X		X	X	X	X	X	
Radiographic Measurements ¹⁵	X				X	X	X	X	X	
Healthcare Economic Outcomes ¹⁶			X		X	X	X	X	X	
General Satisfaction Questionnaire										
Study Exit										X

¹ Baseline visit study activities must occur within 90 days of the Index Procedure unless otherwise noted.

² BMI should be calculated from height and weight measurement to determine subject eligibility.

³ Blood collection is required only if subject has diagnosis of diabetes to determine fasting plasma glucose levels or HbA1c.

⁴ 4-point monofilament test is required only if subject has diagnosis of diabetes or if warranted by PI to assess for peripheral neuropathy.

⁵ Three radiographic views of the operative foot should be obtained per visit (weight-bearing AP, lateral and axial views of operative foot). The axial view should be collected using the study provided axial positioner.

⁶ QOL assessment tools – MoxFQ and PROMIS-29 (PROMIS-25 for ages 14-17) and Sports Questionnaire

⁷ Pregnancy test, if applicable, completed within 7 days of Index Procedure. May be completed on day of Index Procedure.

⁸ For the purposes of determining IMA, HVA and MMA for subject eligibility, measurements will be made according to institutional SOC. For the purposes of all data analysis, measurements made by the Central Radiologist will be utilized. If there are minor differences in baseline IMA, HVA and MMA measurements made by the central radiologist, the measurements of the PI/site will remain acceptable for determining subject eligibility.

⁹ Confirm exclusion criterion “subject is not a current nicotine user” prior to start of anesthesia. If subject indicates current use of nicotine, subject should be considered a screen failure.

¹⁰ If subject requires an incision >4.0 cm to complete the Lapiplasty® Procedure, the subject should be considered a screen failure.

¹¹ Documentation for return to weight bearing activities include time to start weight-bearing in boot, time to start weight-bearing in shoe, and time to full unrestricted activity.

¹² ROM - dorsiflexion and plantarflexion should be measured while subject is passive and non-weightbearing with the study provided goniometer.

¹³ Secondary surgical interventions, Wound healing requiring intervention, infection requiring intervention, hardware removal, revision procedure of 1st ray, other complication requiring surgical intervention.

¹⁴ Only AEs related to the Lapiplasty® Index Procedure or the Lapiplasty® System Implants will be recorded on the eCRF.

¹⁵ Radiographic Measurements are completed by the Central Radiologist only.

¹⁶ Healthcare Economic Outcomes, see Secondary Endpoints for data to be recorded on eCRF.

Sample Size

There is no formal sample size calculation as this is a single arm study and is descriptive in nature. A sample size of 200 patients is chosen, ensuring the feasibility of the study as clinical findings suggest that the bunion recurrence rate after the Lapiplasty® Procedure is low.

6 General Analysis Considerations

All analyses will be performed using SAS software, version 9.4 (SAS Institute Inc., Cary, NC).

6.1 Baseline

Baseline values are those which were collected at the Baseline visit (Visit 1). If a baseline value is missing, then the most recent value collected within 90 days prior to the Index Procedure will be used.

6.2 Analysis Populations

6.2.1 Intent-to-Treat Population

The Intent-to-Treat (ITT) population is defined as all enrolled subjects who met inclusion/exclusion criteria and were treated with the Lapiplasty® Procedure using the Mini-Incision System.

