#### 4.0 INVESTIGATIONAL PLAN

##### 4.1 Overall Study and Design – Subject Disposition Diagram

## Overall Study and Design – Description

Patients 14 years through 58 years with symptomatic hallux valgus will be eligible to participate based on the inclusion and exclusion criteria defined in this protocol.

The overall plan for all subjects consists of the following elements:

- Patients will be informed about the nature of the research, given the ICF to read, and if the patient understands and agrees to the procedure, they will be asked to provide written informed consent. Subjects are considered **enrolled** in the study when they have signed an informed consent;
- Subjects will undergo screening procedures during the baseline visit to determine if inclusion and exclusion criteria are satisfied and the subject is eligible for the study procedure;
- Subjects must meet all inclusion/exclusion criteria before being **treated** in the study. If any eligibility criteria (including intra-operative criteria) are not satisfied, the subject will be considered a screen failure and will not be considered treated in the study;
- Subjects will undergo the Lapiplasty® Procedure, per protocol. Subjects are considered **treated** in the study when biplanar plating at the TMT joint is complete **and** the incision length is confirmed to meet criteria;
- Subjects will be followed for up to 2 years post index procedure to evaluate outcomes and potential complications;
- Subjects will be assessed for AEs and will be instructed to notify the PI of any AEs that occur during the entire course of the study. Data will be recorded into subject source medical records.

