### 4.2.2 Enrollment and Treatment

- Subjects are considered **enrolled** in the study once the informed consent has been signed by the patient. Subjects who sign a consent document, but do not meet inclusion/exclusion criteria (including intra-operative criteria) will be considered a screen failure. Subjects are considered **treated** in the study when the biplanar plating is complete **and** the incision length is confirmed to meet criteria.

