## 7.2 Visit 2 –Index Procedure

The following must be conducted:

- Exclusion Criteria (confirm patient has abstained from nicotine use prior to anesthesia)
- Medical History [if relevant medical history (e.g., related to bone quality or patient condition that does not exclude them from participation in study) is identified during index procedure]
- Foot Measurements
- Index Procedure
  - Start and stop time of tourniquet placement
  - Time of first incision and placement of final plate screw
  - Length of incision at start of procedure
  - Extension of incision and location of extension (proximal, distal or both), as applicable
  - Completion of lateral release
  - Use of SpeedSeeker™ device (or fulcrum and joint seeker)
  - Total length of time of use of Mini-Incision™ Positioner
  - Use of Mini-Incision™ Cut guide
  - Joint morphology of articular surface (uni-facet, bi-facet, or tri-facet), if feasible
  - Use of Compressor device
  - Use of Mini-Incision™ System
  - Use of Transverse Screw and location of screw placement, if applicable
  - Use of Interfrag Screw at TMT joint, if applicable
  - Use of additional plate screws (Long Screw Pack, FastPitch™ Screw Pack, other), if applicable
  - Use of Headless Screw for Akin procedure, if applicable
  - Length of incision after suturing complete
    - If incision required extension beyond >4.0 cm to complete Index Procedure, the subject will be treated as a screen failure.
- Digital photograph of operative foot, post-incision, not required
- Post-op surgical dressing/protection utilized
- Concomitant Procedures performed
- Deviations/Delays to Normal Operative Plan
- Medications Review (Pre-operative and Post-operative)
- Adverse Events Assessment, including Intra-Operative Procedural Complications
- Post-op Care instructions review
  - Post-op mobility assistance device utilized
- Post-op Weight-Bearing protocol instructions review

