### **9.3 Analysis Population**

Intent-to-Treat (ITT) population: The ITT population is defined as all enrolled subjects who were treated with the Lapiplasty® Procedure using the Mini-Incision™ System.

Per-Protocol (PP) Population: The per-protocol population is defined as all enrolled subjects who were treated with the Lapiplasty® Procedure using the Mini-Incision™ System who did not experience a major protocol violation. Major protocol violations include, but are not limited to, subjects who:

- Entered the study although they did not satisfy the eligibility criteria;
- Completed incorrect version of PROMIS based on age of subject;
- Did not return to protective weight-bearing activities by 3 weeks (+3 days);
- Received Lapiplasty® Procedure (or other hallux valgus procedures) on contralateral foot less than 6 months after initial index procedure; or
- Developed withdrawal criteria during the study but were not removed from study participation.

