7.1 Study Subjects

7.1.1 Subject Disposition

All subjects who signed informed consent will be included in the subject disposition table. The number and percentage of subjects enrolled, screened, screen failed, treated, anesthetized but not treated, completed, and discontinued (including reason for discontinuation) will be summarized. Subjects are considered enrolled in the study when they have signed an informed consent. Subjects will undergo screening procedures during the baseline visit to determine if inclusion and exclusion criteria are satisfied and the subject is eligible for the study procedure. If any eligibility criteria (including intra-operative criteria) are not satisfied, the subject will be considered a screen failure and will not be considered treated in the study. Subjects are considered treated in the study when biplanar plating at the TMT joint is complete and the incision length is confirmed to meet criteria.

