7.3 Safety and Health Economic Outcomes Analysis

The ITT population will be used for all safety and health economic analyses. Statistical summaries will be produced in accordance with section 7, and listings will be generated by site, subject, and visit within subject. For the purposes of this analysis, coding dictionaries will not be utilized.

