7.5 Exploratory Analysis

Additional endpoints may be pursued at the time of analysis and will be exploratory in nature.

Quality Assurance of Statistical Programming

Clinical operations will independently validate the safety analyses (adverse events and clinical complications). A second statistician will independently reproduce the primary, secondary, health economic, and summary statistics.

To provide high quality code that is understandable and allows for reproduction of the analysis, the following points will be followed:

- The population to be used in a table or listing will be explicitly set at the start of a block of code that computes the output.
- All outputs will include the date and time that the output was generated, and the name of the code file that produced the analysis.
- At the start of any code file, there will be a set of comments that provide the following information: author, date, references to inputs and outputs, reference to any parent code file that runs the child code file.

Summary of Changes to the SAP

N/A

References

- ¹ Ranging from 3.6%-78% recurrence at an average of 2.4-14 years post-surgery.
- ² Shurnas PS, et al. Foot Ankle Int. 2009. 30: 865-872.
- ³ Jeuken RM, et al. Foot Ankle Int. 2016. 37:687-95.
- ⁴ Kim Y, et al. A New Measure of Tibial Sesamoid Position in Hallux Valgus in Relation to the Coronal Rotation of the First Metatarsal in CT Scans. Foot Ankle Int. 2015; 36:944-52.
- ⁵ Okuda R, et al. The Shape of the Lateral Edge of the First Metatarsal Head as a Risk Factor for Recurrence of Hallux Valgus. J Bone Joint Surg Am. 2007; 89:2163-72.
- ⁶ Okuda R, et al., Postoperative Incomplete Reduction of the Sesamoids as a Risk Factor for Recurrence of Hallux Valgus. J Bone Joint Surg Am. 2009; 91:1637-45.
- ⁷ Catanzariti AR, et al. J Foot Ankle Surg. 1999. 38:325-332.
- ⁸ Galli SH, et al. Foot & Ankle Orthopaedics. 2020. 5(2) 1-2.
- ⁹ Ray JJ, et al., Multicenter Early Radiographic Outcomes of Triplanar Tarsometatarsal Arthrodesis with Early Weightbearing. Foot Ankle Int. 2019; 40(8):955-960.

Table of Contents of Statistical Outputs

TLF #	Title
Table 1	Subject Disposition, ITT Population
Table 2	Demographic, Baseline, and Intra-Operative Characteristics, ITT Population
Table 3	Proportion of subjects with recurrence of hallux valgus deformity at 12- & 24- months post-procedure, ITT Population
Table 4	Proportion of subjects with successful correction at 6 weeks post-procedure, ITT Population

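### The ITT is the only safety set and leaves out operated patients whose incision had to exceed 4.0 cm, so their adverse events have no planned summary; the documents also disagree on ineligible treated patients

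*SAP*

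**What the plan says.** **Who counts as treated.** Protocol 4.2.2 grants treated status only when biplanar plating is complete and "the incision length is confirmed to meet criteria". Protocol 4.1 states the general rule: "If any eligibility criteria (including intra-operative criteria) are not satisfied, the subject will be considered a screen failure and will not be considered treated". Exclusion criterion 24 (incision above 4.0 cm) may be determined before or during the operation. In Protocol 7.2 the rule sits directly under the item for incision length once suturing is complete: "If incision required extension beyond >4.0 cm to complete Index Procedure, the subject will be treated as a screen failure". SAP 1.3, 1.5 (footnote 10) and 7.1.1 repeat these rules.

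**Analysis sets.** Protocol 9.3: "The ITT population is defined as all enrolled subjects who were treated with the Lapiplasty® Procedure using the Mini-Incision™ System". SAP 6.2.1 instead has "all enrolled subjects who met inclusion/exclusion criteria and were treated with the Lapiplasty® Procedure using the Mini-Incision System". Both documents then list entry despite unmet eligibility criteria as the first reason for removal from the per-protocol (PP) set.

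**Safety.** SAP 7.3: "The ITT population will be used for all safety and health economic analyses". Protocol 9.4 says the same, and SAP 6.2 defines no other safety set. Protocol 9.7, however, has related AEs listed and summarized over all subjects.

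**Disposition.** SAP 7.1.1: "All subjects who signed informed consent will be included in the subject disposition table", with counts that include screen failures and subjects anesthetized but not treated. The SAP's list of statistical outputs titles Table 1 "Subject Disposition, ITT Population".

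**The concern.** Needing a longer incision is something that happens in the course of the technique under study. Using it to decide who is in the safety set selects patients after exposure. A single-arm study has no comparator that would reveal the effect.

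Three things are at stake:
- **Safety denominator.** Patients who had the operation and the positioner can drop out of the AE, serious AE and complication tables.
- **Two secondary endpoints.** Endpoint 10 (change in incision length) cannot show a final length above 4.0 cm, because anyone above it has been removed. Endpoint 14 (positioner time against necrosis, blistering, bruising and ulceration) loses converted patients who were exposed to the positioner.
- **Which ITT is reported.** The SAP's added eligibility condition leaves its own first PP exclusion with nobody to remove. The PP sensitivity analysis runs only if the two sets differ considerably, so moving ineligible subjects out of the ITT makes that check less likely to be triggered.

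**Working it through.** The plan states no figure on this point: there is no formal sample size calculation, conversion rate or AE rate. The check is therefore set logic first, followed by an illustration of size.

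**Step 1. Trace a patient whose incision is extended beyond 4.0 cm.**
1. Consent signed: enrolled (Protocol 4.2.2).
2. Incised, positioner applied, plated, sutured; final length found to exceed 4.0 cm: screen failure (Protocol 7.2; SAP 1.5, footnote 10).
3. Screen failure: not treated (Protocol 4.1; SAP 7.1.1).
4. Not treated: outside the ITT under Protocol 9.3 and under SAP 6.2.1.
5. Outside the ITT: outside all safety analyses (Protocol 9.4; SAP 7.3). Tables 17–20 carry the ITT label. Table 25 has no label but falls under SAP 7.3.

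The loss comes from the definition of treated. It occurs with or without the eligibility phrase in SAP 6.2.1.

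**Step 2. Trace a patient who was operated on and later found ineligible on some other criterion.**

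| Text | In the ITT? |
|---|---|
| Protocol 9.3 alone | Yes; removed only at the PP step |
| Protocol 4.1 read with 9.3 | No; classed as not treated |
| SAP 6.2.1 | No; eligibility is a condition of the ITT |

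SAP 6.2.2 builds the PP set from the ITT, so its ineligibility exclusion is empty. Read with Protocol 4.1, the same exclusion in Protocol 9.3 is empty too. The bullet has a function only if ineligible subjects can be in the ITT.

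**Step 3. Table 1.** Restricted to the ITT, the counts for screen failures and for anesthetized but not treated would both be zero by definition. SAP 7.1.1 plainly intends otherwise.

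**Step 4. Size (illustrative).** The protocol synopsis caps *treated* subjects at 200, so converted patients come on top of the 200. With conversion rate *c*:

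attempted = 200 / (1 − *c*); converted = attempted − 200.

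Assume an AE proportion of 10% in treated patients and *RR* times that in converted patients:

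all-attempted AE proportion = (200 × 0.10 + converted × 0.10 × *RR*) / attempted.

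| *c* (assumed) | Attempted | Converted | Exact 95% CI for conversion (whole numbers) | AE proportion, *RR* = 1 / 2 / 3 | Patients with an AE left out, *RR* = 1 / 2 / 3 |
|---|---|---|---|---|---|
| 2% | 204.1 | 4.1 | 4/204: 0.5–4.9% | 10.0 / 10.2 / 10.4% | 0.4 / 0.8 / 1.2 |
| 5% | 210.5 | 10.5 | 11/211: 2.6–9.1% | 10.0 / 10.5 / 11.0% | 1.1 / 2.1 / 3.2 |
| 10% | 222.2 | 22.2 | 22/222: 6.3–14.6% | 10.0 / 11.0 / 12.0% | 2.2 / 4.4 / 6.7 |

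The ITT tables would show 10.0% in every row, and no incision above 4.0 cm.

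**The case against.** **Conversions are not invisible.** A reader might infer that they go wholly unreported. They do not: SAP 7.1.1 counts screen failures and subjects anesthetized but not treated among all who consented, and a converted patient falls there. What stands is narrower. Those counts pool other reasons, and no conversion rate or interval is planned.

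**Harms are captured at source.** AEs, including intra-operative complications, are assessed at Visit 2. Protocol 7.12 asks for positioner damage to be recorded as an AE and a product complaint. The reporting routes for related serious AEs and for product complaints are not limited to the ITT, and Protocol 9.7 refers to all subjects. The gap is in the planned summary, not in collection on the day of surgery.

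**The protocol does not clearly keep ineligible patients.** A reader might conclude that the SAP drops patients whom the protocol retains. That is true of Protocol 9.3 alone; Protocol 4.1 already classes them as not treated. The conflict lies within the protocol as well as between the two documents.

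**The effect on rates may be small.** Even at 10% conversion and three times the AE risk, the illustrative proportion moves from 10% to 12%, well inside the exact 95% CI for 20/200 (6.2–15.0%). This stands as a limit on size. It does not excuse an incomplete denominator.

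**The 4.0 cm criterion is prospective, and technical failure is not among the four study objectives.** Both are correct. But change in incision length and positioner injury are listed secondary endpoints, and both are truncated.

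**Conclusion.** The point holds in this form. Followed as written, the SAP gives no AE summary for operated patients converted to an incision above 4.0 cm. It shows them at most within an unspecific disposition count, and it leaves them out of the incision-length and positioner-injury endpoints. That conflicts with Protocol 9.7. The ITT definitions in Protocol 4.1, Protocol 9.3 and SAP 6.2.1 do not agree on ineligible treated patients, and the title of Table 1 contradicts SAP 7.1.1.

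The omission follows from the definitions at any non-zero conversion rate. Its size is unknown: about 4–22 operated patients per 200 treated at an assumed 2–10% conversion. The effect on AE proportions depends entirely on assumed rates and is nil if converted patients have the same AE risk as the rest.

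A reader might also infer that the primary recurrence result is made to look better. The documents do not support that: nothing in them links a longer incision to recurrence.

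**What to change.** 1. **Safety population.** Define it as all subjects with a skin incision for the index procedure, and run Tables 17–20 and 25 on it. Show converted subjects separately with their actual follow-up, at minimum the intra-operative AEs already collected at Visit 2, so that short follow-up does not dilute the 24-month rates. State whether later AEs are collected for them; the documents describe no follow-up after a screen failure.
2. **Conversion.** Report the number converted to above 4.0 cm over all incised subjects, with an exact 95% CI, as its own line in disposition. Include their incision lengths in Table 13.
3. **One ITT definition.** Reconcile Protocol 4.1, Protocol 9.3 and SAP 6.2.1, removing ineligible treated subjects only at the PP step. Deleting the eligibility phrase from SAP 6.2.1 is not enough, because SAP 1.3 repeats the Protocol 4.1 rule. Since criterion 24 is itself an eligibility criterion, say explicitly where converted subjects fall. Reconcile Protocol 9.4 and SAP 7.3 with Protocol 9.7.
4. **Table 1.** Retitle it for all consented subjects, to match SAP 7.1.1.

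None of this touches the 4.0 cm rule or surgical conduct. Items 1, 2 and 4 need SAP text and somewhat more programming, using data that Visit 2 already records. Item 3 also needs protocol wording aligned, and collecting later AEs in converted subjects could need a protocol change if it is not already done. The safety figures may become less favourable.
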